6. SPECIFIC AIMS

The proposed study is a randomized, double-blind, placebo-controlled dose-ranging, pilot study intended to replicate and extend the promising results from an earlier proof of concept study testing intranasal oxytocin in schizophrenia. This second-stage pilot study will seek to obtain information not obtained in the limited proof-of-concept study; specifically, the optimal dose of oxytocin for efficacy and tolerability, the time to optimal efficacy and the effects of longer term exposure (6 weeks) to daily intranasal oxytocin. It is expected that the information obtained from this pilot study will provide indispensable information for the design and execution of future full scale parallel arm studies to test the efficacy and safety of intransal oxytocin. It may also provide valuable information for other pilot studies that may test oxytocin in other clinical populations, and ultimately for the development of new treatment strategies for psychosis and other mental disorders based upon the use of oxytocin or oxytocin analogs.

Specific Aim #1:To replicate the promising positive findings from the pilot study in a larger and more diverse sample of subjects recruited from more than one site. In the recent pilot-study mentioned, 80 IU of intranasal oxytocin significantly improved positive and negative symptoms of schizophrenia and short term memory recall. However that study was conducted in a small number of subjects using a crossover experimental design. These findings are very promising but need to be replicated with a larger number of subjects representing more than one recruitment site.

Specific Aim #2: To investigate the efficacy and safety of higher doses of oxytocin. The original study used 80 IU of intranasal oxytocin and this was found to be well tolerated and effective. However the effect size in this study was moderate. It is possible that higher doses of oxytocin would produce stronger therapeutic effects; therefore, this study proposes to test a higher dose of oxytocin, 168 IU, in addition to the approximate dose tested in the pilot study.

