Sample Size Calculation. The primary efficacy measure will be change in PANSS total score from baseline to each visit. Based upon a preceding proof-of-concept study (Feifel et al. Biological Psychiatry, in press) with effect sizes (cross-over design) range from .40 to .53. An estimated sample size of 24 in the placebo group and 48 in the oxytocin group (24 in each dose group) is required to achieve 85% power to detect an effect size of 0.3 for time-averaged main treatment effect (Cohen's d for standardized mean difference between oxytocin and placebo treatment groups) using 6 repeated measurements having a AR(1) (first order autoregressive) covariance structures and assuming the correlation between observations on the same subject is 0.5, and the alpha level (Type I error rate) is 0.05 in a 2-sided test (Hintze, 2008). If we ignore the repeated measures design, an effect size of 0.5 will be detected with the same alpha and beta for the same sample size of 80 patients in the ratio of 2:1 for oxytocin:placebo.

The proposed sample size includes considerations for a single pre-specified, planned interim analysis for futility stopping based on conditional power (CP) (stochastic curtailing method) (Halperin et al., 1982; Lan et al., 1982) or an equivalent stopping boundary on interim Z-test value (B-value) (Lan and Witts, 1988). This interim futility analysis will be performed and reviewed by an external statistical consultant [name] when 50% of the enrolled patients complete 6 weeks of follow-up. The adjusted critical value for an overall alpha of 0.05 (2-sided) in the final analysis is 0.0515 with resulting power 84.6% to detect a specified effect size of 0.3 or greater with 80 patients in the ratio of 2:1 for oxytocin:placebo (See Interim Analysis Plan below).

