Analysis Methods: The primary population for efficacy analyses includes all randomized subjects based on the intention-to-treat principle. The population for safety analyses will include all subjects who receive at least one dose of study medication. In the primary analysis, we test the hypothesis of difference in PANSS total change score (Week 6) between the combined oxytocin and placebo groups with adjustment for baseline score using a likelihood-based mixed-effects model for longitudinal data analysis (MMRM LDA) (Fitzmaurice and Ware, 2004). The MMRM LDA model can accommodate incomplete data under the assumption of ignorable attrition (see below under Missing Data). The same MMRM LDA model will be applied to evaluate the dose-response relationship using a linear contrast for the placebo and oxytocin dose groups, comparisons of treatment groups over time using treatment-by-visit (categorical visit variable) interaction term, and the trajectories of treatment responses over time based on time slope computed for each subject (continuous time variable).

Secondary efficacy measures will be the PANSS positive symptom and negative symptom subscales, PANSS general psychopathology subscale, CGI-S, CGI-I HAM-A, CCDS, GAF, cognitive scales as with the primary endpoint using the same MMRM LDA analyses. No multiplicity adjustment will be made in the secondary analyses. Appropriate descriptive statistics with 95% confidence intervals will be provided within and across treatment groups. Normal assumption will be checked and nonparametric alternatives will be considered if the assumption is seriously violated.

Mediators and baseline moderators of treatment effects on efficacy outcome measures will also be explored (Kraemer et al., 2006). The significance of moderator effects due to baseline characteristics (age, gender, initial

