PANSS scores, duration of illness, class of medication) will be tested using treatment-by-baseline characteristic interaction terms in the MMRM LDA and/or ANCOVA models. To assess impact of improvement in one domain (e.g. positive symptoms) on the efficacy of a related symptom domain (e.g. negative symptoms), a mediator analysis model with terms for treatment, baseline, and positive symptoms improvement will be applied to determine significance of oxytocin effect on reductions in negative symptoms after adjustment for potential positive symptom improvement. We will perform similar mediator analysis for assessing inter-relationships between cognitive improvement and symptom improvement in positive and/or negative symptoms. In addition, cross-sectional baseline and longitudinal change score associations between treatment outcome measures and mediator effects will be assessed by including mediators as time-varying covariates in the MMRM LDA models (Diggle et al., 2001).

MU-Suppression. Data will be analyzed in two ways. Pearson rank correlations will be used to examine correlations between mu wave suppression in response to a single dose of OT and symptom severity at the end of 6 weeks of treatment. In additional exploratory analyses, mu suppression values will be split at the median into High suppressors and Low suppressors and followed up by correlations with symptom measures to determine if initial high suppression is correlated with greater improvement in symptom severity. Secondarily, Pearson rank correlations will be conducted between mu wave suppression and symptom severity at baseline, and between mu wave suppression and symptom severity after administration of a single dose of oxytocin.

Safety Endpoints. The safety dataset will contain all subjects who take at least one dose of oxytocin. All adverse events will be coded using the most current version of the Medical Dictionary for Regulatory Activities (MedDRA). The number and percentage of subjects reporting treatment-emergent adverse events will be tabulated within each dose group by treatment, system organ class (SOC) and MedDRA-preferred term. Treatment-emergent adverse events will be those adverse events that begin or worsened following the first dose of study drug. Adverse events will be further classified by severity and investigator-assigned relationship to study drug.

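### The planned mediator model tests the oxytocin effect on negative symptoms after adjusting for positive-symptom improvement, with no time order or control of shared causes, so a wholly direct effect can look partly or largely mediated

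*Combined protocol and SAP*

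**What the plan says.** In the combined protocol and SAP, section 9, Analysis Methods, the topic is introduced as exploratory: "Mediators and baseline moderators of treatment effects on efficacy outcome measures will also be explored". For the question whether gains in one symptom domain account for gains in another, "a mediator analysis model with terms for treatment, baseline, and positive symptoms improvement will be applied", and its purpose is to "determine significance of oxytocin effect on reductions in negative symptoms after adjustment for potential positive symptom improvement". The same approach is to be used between cognitive and symptom improvement. A further analysis looks at baseline and longitudinal associations "by including mediators as time-varying covariates in the MMRM LDA models".

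No visit or lag is given for the mediator in either analysis. Nothing is said about shared causes of the two changes, or about an estimate of the indirect effect with an interval. The Missing Data paragraph defers further detail to a Statistical Analysis Plan, but the topics it names are the mixed-model methodology, sensitivity analyses and assumptions. Mediation is not among them.

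The description of the primary outcome measure shows that the positive and negative subscales are parts of one PANSS. The Study Procedures table has the PANSS at baseline and at every weekly visit, whereas cognitive testing on treatment occurs only at Week 6 or early termination.

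**The concern.** Randomisation protects the comparison of negative-symptom change between arms. It does not protect that comparison once it is conditioned on a variable that treatment may itself have changed. Two subscales rated in one interview can move together for reasons unrelated to any causal path from one to the other, such as general clinical state, a rater's overall impression, or adherence to the background antipsychotic. The adjusted model credits that co-movement to the mediator and takes it away from the treatment term.

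The plan judges the result by whether the treatment term stays significant. An effect on negative symptoms that owes nothing to positive symptoms could lose significance and be put down to them. That would matter in a pilot meant to inform later full-scale studies.

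**Working it through.** The plan states no figure for this analysis, so there is none to reproduce. The check asks what the planned model returns when nothing is mediated.

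**Inputs from the documents**
- Arms: "An estimated sample size of 24 in the placebo group and 48 in the oxytocin group (24 in each dose group) is required", so 24 v 48, N=72; two-sided alpha 0.05 (section 9, Sample Size Calculation).
- Effects: the earlier study found that "80 IU of intranasal oxytocin significantly improved positive and negative symptoms of schizophrenia and short term memory recall" (section 6, Aim 1). Its "effect sizes (cross-over design) range from .40 to .53", but these are not assigned to subscales.
- Serial correlation: 0.5 with an AR(1) structure (section 9). This is correlation over time, not between domains.

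**Assumed, because the documents do not give them:** rho (residual correlation of positive and negative change), dP and dN (effects on positive and negative change, in residual SD units).

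**Step 1. Bias with no mediation.** Let P = dP·T + e1 and N = dN·T + e2, with corr(e1, e2) = rho and no path from P to N. Adjusting N for P gives a treatment coefficient of dN − rho·dP. The true direct effect is dN, so the falsely mediated share is rho·dP/dN.

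| dP | dN | rho 0.2 | rho 0.3 | rho 0.5 | rho 0.7 |
|---|---|---|---|---|---|
| equal | equal | 20% | 30% | 50% | 70% |
| 0.5 | 0.3 | 33% | 50% | 83% | 117% |
| 0.3 | 0.5 | 12% | 18% | 30% | 42% |
| 0 | any | 0% | 0% | 0% | 0% |

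For dN = 0.30 and dP = 0.40, the adjusted term is 0.30 − 0.3 × 0.40 = 0.18, 0.30 − 0.5 × 0.40 = 0.10, or 0.30 − 0.7 × 0.40 = 0.02. Least-squares simulation with 24 v 48 (4,000 replicates per setting) agrees with the formula.

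**Step 2. Effect on significance.** In simulation with dP = dN = 0.5, the chance of a significant treatment term falls on adjustment from about 50% to 28% (rho 0.3), 20% (rho 0.5) or 13% (rho 0.7), with no mediation at all.

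**Step 3. Does time order alone cure it?** Take equal effects at both times.
- If serial correlation decays as AR(1) from 0.5, a three-visit lag gives a factor of 0.5³ = 0.125. The false share becomes rho × 0.125, or 2.5% to 9% for rho 0.2 to 0.7.
- If the correlation stays at 0.5 at every lag, the share is rho × 0.5, or 10% to 35%.

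A lag reduces the bias but need not remove it.

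**Step 4. Adding Week 3 negative change.** Let r be the serial correlation between Weeks 3 and 6, and let the cross-domain correlation over that gap be r·rho. Regressing Week 6 negative change on treatment, Week 3 positive change and Week 3 negative change gives a coefficient of (r·rho − rho·r)/(1 − rho²) = 0 on the positive change. The false indirect path is then 0. The coefficient on Week 3 negative change is r, so a direct effect of 0.30 at both visits leaves a treatment term of 0.30 × (1 − r): 0.26 at r = 0.125 and 0.15 at r = 0.5. The zero depends on the assumed cross-domain correlation of r·rho; a shared cause with a different time pattern would leave some bias.

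**The case against.** Four arguments can be made for leaving the text alone, and one against the remedy.

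- **Size.** A reader might infer that a direct effect will always look largely mediated, or that the result depends only on the correlation between subscales. The documents do not support either. They give no rho and no separate subscale effects. With equal effects and rho of 0.2 to 0.3 the share is 20% to 30%, and it is zero at any rho if positive symptoms do not respond. Both dP and dN are drug effects. This objection stands.
- **Timing.** The plan does not specify a same-visit model; it is silent on timing. That is so, and the silence leaves the same-visit model open.
- **Time-varying analysis.** The plan already describes this as a study of associations. That is correct, and the fix only makes the limit explicit. The model tested for significance after adjustment carries no such limit.
- **Status.** The analysis is exploratory, in a pilot, and the primary PANSS total test is unaffected. This limits the consequence but does not make the adjusted test answer its question.
- **The remedy also adjusts for a post-randomisation variable.** Step 4 confirms that this lowers the treatment term. It is acceptable only if that term is not read as the total direct effect. Aim 3 in section 6 expects benefit to grow from Week 3 to Week 6, so a Week 3 mediator will miss later change. A cognitive mediator cannot be lagged at all, because it has only one on-treatment measurement.

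**Conclusion.** The concern holds in conditional form. If oxytocin moves positive symptoms and the two residual changes are positively correlated, the planned adjusted test understates a direct effect on negative symptoms by a share of about rho × dP/dN. Under the stated assumptions that is 20% to 70% for equal effects and rho 0.2 to 0.7. It is more if the positive effect is the larger, less if it is the smaller, and nil if positive symptoms do not respond. These conditions are plausible here: the protocol reports improvement in both domains in the earlier study and itself calls them related. Missing time order is only part of the cause, because shared influences produce the same bias and can survive a lag.

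Loss of significance after adjustment is therefore not evidence of mediation, and the plan has no means of telling the two apart. The text should be changed, but the consequence is confined to interpreting exploratory results.

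**What to change.** 1. State in section 9 and in the Statistical Analysis Plan that three kinds of model describe association only: same-visit adjusted models, time-varying-covariate models, and every model with a cognitive mediator. Add that no conclusion about mediation will be drawn from the significance of the adjusted treatment term.
2. For the exploratory positive-to-negative question, use the weekly PANSS to set time order: positive change at Week 3 as mediator and negative change at Week 6 as outcome. Adjust for baseline positive, baseline negative and Week 3 negative change. Report the indirect path explicitly, with a bootstrap 95% interval.
3. State that the treatment term of that model is not the total direct effect, because it leaves out effect carried through Week 3 negative change.

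The cost is plan wording and modest programming; no new data are needed. Three limits should be stated with it: intervals will be wide at N=72, mediation through positive change after Week 3 is missed, and unmeasured shared causes may remain.

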Specific Aim #3:Establish the time needed to reach peak efficacy. Duration of treatment in the original study was three weeks, and significant therapeutic benefit was observed only at the three-week endpoint but not earlier. In the proposed study, subjects will receive study drug for 6 weeks and we expect that the size of the therapeutic benefit of oxytocin will increase from 3 to 6 weeks.

Specific Aim # 4: Investigate the possible cognitive effects of intranasal oxytocin. In the pilot study, oxytocin significantly improved short term recall performance in the California Verbal Learning Test. This raises the possibility that chronic oxytocin will improve cognitive deficits associated with schizophrenia. This study will test this hypothesis using the Computerized Multiphasic Interactive Neurocognitive DualDisplay™ System (CMINDS®) and Mayer-Salovey-Caruso Emotional Intelligence Test: Managing Emotions (MSCEIT™ ME).

Specific Aim #5: To determine if daily intranasal oxytocin is sufficiently safe, feasible and acceptable to patients to warrant further clinical development. Information derived from this study will inform development of oxytocin not only for schizophrenia but other potential neuropsychiatric disorders.

Specific Aim #6: The objective of the study is to compare the efficacy of intranasal oxytocin versus intranasal placebo to improve symptoms in schizophrenia patients who have residual symptoms despite being on adequate treatment with antipsychotic medication. Improvement will be measured by total score in the Positive and Negative Syndrome Scale (PANSS).

Specific Aim #7: To determine if oxytocin-induced enhancement of mu-rhythm suppression of 'mirror' neurons in schizophrenia patients can serve as a predictive biomarker of individual clinical response to this neurohormone.

Secondary objectives include:

 To evaluate the efficacy of intranasal Oxytocin as measured by change in the total CGI-Severity and Improvement scores

- To evaluate the efficacy of intranasal Oxytocin as measured by change in the total GAF score
- To evaluate the efficacy of intranasal Oxytocin as measured by change in the total scores of HAM-A.
- To evaluate the efficacy of intranasal Oxytocin on self-rated social anxiety as measured by change in the total Social Phobia Inventory (SPIN).
- To evaluate the efficacy of intranasal Oxytocin as measured by change in the total Calgary Depression Scale for Schizophrenia (CDSS) scores.

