thought to index the activity of 'mirror' neurons. Mu rhythms, measured from this brain region show reliable, dose dependent, suppression when the subject perceives biological motion (but not non-biological motion). Thus, mu wave suppression is an easily quantifiable operational measure of the neural processing of biological motion. In a recently published study conducted in [name] laboratory, the applicant showed that neural mu wave suppression induced by biological motion is impaired in first-episode of psychosis subjects, and that the neural impairment is inversely correlated with negative symptoms and social adjustment, providing construct validity for the mu suppression paradigm as an operational measure of social cognition in patients with psychosis (Singh, et,al, 2010).

Given OT's strong implication in social perception, it would be reasonable to expect that exogenous OT affects mu wave suppression in the context of biological motion. This has been in fact, confirmed in a recent study by Keri et al. using a well-established paradigm of biological motion similar to that used by our group. Keri et al, demonstrated that intranasal OT significantly enhanced detection of biological motion (human form) but not non-biological motion (rotating circle) compared to intranasal placebo. Taken together, the applicant's study and that by Keri et al, demonstrate that patients with psychosis have impaired biological motion induced mu suppression compared to normal subjects and that intranasal OT enhances this neural process in normal subjects. It is reasonable to expect that intranasal oxytocin will improve mu suppression in schizophrenia patients and we expect to demonstrate this. We also expect to find that subjects with the greatest enhancement in mu suppression are more likely to experience clinical improvement in response to 6-weeks of oxytocin treatment.

Hypothesis: We hypothesize that augmentation of antipsychotics with intranasal oxytocin will significantly improve psychopathology ratings as compared to placebo and an improvement in certain cognitive functions may be also observed.

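### Aim 7 asks for a predictive biomarker, but no mu analysis has a treatment-by-mu term or compares arms, so a marker that is only prognostic, or only tracks baseline severity, can look predictive.

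*Combined protocol and SAP*

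**What the plan says.** Section 6, Aim 7, asks whether oxytocin-induced enhancement of mu suppression "can serve as a predictive biomarker of individual clinical response to this neurohormone". Section 7 states the expectation that "subjects with the greatest enhancement in mu suppression are more likely to experience clinical improvement in response to 6-weeks of oxytocin treatment".

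Section 9, MU-Suppression, gives the analyses:

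- **Lead:** "correlations between mu wave suppression in response to a single dose of OT and symptom severity at the end of 6 weeks of treatment". No baseline adjustment is given, and the arms that enter are not named.
- **Exploratory:** a median split into high and low suppressors, followed by correlations with symptom measures "to determine if initial high suppression is correlated with greater improvement in symptom severity".
- **Secondary:** correlations of mu suppression with severity at baseline and with severity after the single dose.

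The plan already has a way to test effect modification. In Analysis Methods, moderator effects "will be tested using treatment-by-baseline characteristic interaction terms in the MMRM LDA and/or ANCOVA models". The listed moderators are age, gender, initial "PANSS scores, duration of illness, class of medication". Mu response is not among them.

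**The concern.** A prognostic marker tells us who will be better or worse at Week 6 whatever they receive. A predictive marker tells us for whom oxytocin differs from placebo. Aim 7 asks the second question, and only a comparison of the marker's slope between arms answers it. None of the planned mu analyses makes that comparison.

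The lead correlation has a further weakness. Patients who are severe at baseline tend to be severe at Week 6, so any association between mu and baseline severity carries through to the Week-6 score. Such an association is plausible: section 7 reports, for impaired mu suppression in first-episode psychosis, that "the neural impairment is inversely correlated with negative symptoms and social adjustment". At stake is an aim-level statement about who responds to the drug, which could rest on a correlation containing no drug-specific information.

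**Working it through.** The documents give no sample size, power or effect size for the mu analyses, so there is no stated figure to reproduce. The check asks how often the lead correlation is significant when the marker has no treatment-specific effect.

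**Inputs**

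- Randomized: 24 placebo and 48 oxytocin (Sample Size Calculation).
- Sub-study size: participation is optional and no number is given; 36 to 72 is assumed.
- Two-sided 0.05: stated for the primary test, assumed here.
- Within-subject correlation ρ = 0.5 (Sample Size Calculation), used for baseline to Week 6; 0.7 and 0.8 are assumed alternatives.
- Correlation of mu with baseline severity, r_b = 0.2, 0.4 or 0.5: assumed; the documents give none.

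**Marker that only tracks baseline severity.** If mu relates to Week 6 only through baseline, the correlation of mu with Week 6 is r = r_b × ρ. By Fisher's z,

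P(significant) ≈ Φ(√(n−3)·atanh(r) − 1.96) + Φ(−√(n−3)·atanh(r) − 1.96).

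Example: r_b = 0.4 and ρ = 0.5 give r = 0.20. At n = 72, √69 × 0.2027 = 1.684 and Φ(−0.276) = 39%; the other tail is negligible.

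| r_b | ρ | r | n = 72 | n = 36 |
|---|---|---|---|---|
| 0 | any | 0 | 5% | 5% |
| 0.2 | 0.5 | 0.10 | 13% | 9% |
| 0.4 | 0.5 | 0.20 | 39% | 21% |
| 0.5 | 0.5 | 0.25 | 56% | 31% |
| 0.2 | 0.7 | 0.14 | 22% | 13% |
| 0.4 | 0.7 | 0.28 | 66% | 39% |
| 0.5 | 0.8 | 0.40 | 94% | 69% |

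The last three rows are simulated (4000 replicates each); the formula agrees to about one percentage point.

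**Using change instead of level.** With equal variances at both visits, the same marker has correlation −r_b·√((1−ρ)/2) with change. At ρ = 0.5 this is −0.5·r_b, the same size as the correlation with level. This is regression to the mean, and changing the outcome alone does not remove it.

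**Marker prognostic for course equally in all arms.** Take a marker unrelated to baseline, with an assumed slope of 0.3 SD of PANSS per SD of marker. In simulation at n = 72:

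- lead correlation, all arms: significant in 69% of trials;
- lead correlation, oxytocin arms only: 51% to 53%;
- correlation with change, oxytocin arms: 52% to 73%;
- median split on change, oxytocin arms: 34% to 52%.

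**Treatment-by-mu test.** A model with treatment, baseline, mu and treatment × mu rejected in 4.5% to 5.9% of simulated trials across these scenarios, which is the nominal level.

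**Power of that test.** For a slope difference of 0.5 SD at ρ = 0.5, the residual SD is √(1 − 0.25) = 0.866.

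- n = 72: SE ≈ 0.866 × √(1/24 + 1/48) = 0.217, and 0.5/0.217 = 2.31, so power ≈ Φ(2.31 − 1.96) = 64%.
- n = 36: SE ≈ 0.866 × √(1/12 + 1/24) = 0.306, and 0.5/0.306 = 1.63, so power ≈ Φ(1.63 − 1.96) = 37%.

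Simulation, which allows for the t distribution and the sampled marker spread, gives 59% and 30%. For a difference of 0.3 SD it gives 25% and 13%.

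**Feasibility.** Under Study Procedures, the challenge dose and its EEG recordings take place at screening and are not confined to one arm. Randomization follows at Visit 2. Placebo participants in the sub-study therefore have the marker, and the interaction can be fitted.

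**The case against.** The strongest defence is that the plan is less bare than the lead sentence suggests.

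- **Improvement is addressed.** A reader might infer that the plan looks only at end-of-treatment level. The documents do not support that, because the median split is aimed at improvement. It is, however, exploratory and dichotomised, and it has no arm comparison.
- **Baseline severity is examined.** The planned correlation of mu with baseline severity would help to expose a pure severity marker. It stands beside the Week-6 result and is not used to adjust it. It would not expose a marker that is prognostic for course.
- **Placebo patients are not excluded.** It is tempting to say that the placebo arm goes unused. The text does not say which arms enter; what can be said is that no comparison by arm is specified.
- **The cited evidence is indirect.** Section 7 concerns impaired mu suppression in first-episode psychosis, related to negative symptoms and social adjustment. Aim 7 concerns oxytocin-induced enhancement. The documents give no correlation between enhancement and PANSS total, and section 6 lists the mu-severity relation as something to be determined. Confounding is plausible, not established.
- **This is a pilot with an optional sub-study.** The interaction test will often be inconclusive. That supports an exploratory label; it does not make a correlation answer the predictive question.

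These points limit how strongly the concern can be put. They do not supply the missing treatment-by-mu term.

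**Conclusion.** The concern holds in this form: the planned mu analyses cannot separate a predictive marker from a prognostic one, so they cannot support the claim in Aim 7. This follows from the text and does not depend on the simulations.

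How often a misleading result would arise does depend on assumptions. If mu acts only through baseline severity and ρ = 0.5, the lead correlation is significant in 13% to 56% of trials at n = 72 and 9% to 31% at n = 36, for assumed r_b between 0.2 and 0.5. The 94% figure needs the highest assumed value of both correlations and full participation. If mu is unrelated to severity and course, the rate is 5%. A reader might infer that the trial will report a false predictive biomarker; the documents support only that it can.

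Two smaller points stand. The correlations are called Pearson rank correlations, which names no single method, since Pearson's coefficient is not rank-based. The challenge dose that defines the marker is also stated inconsistently: footnote k of the procedures table gives 24 IU for all subjects, and the Visit 1 description gives 24 or 48 IU.

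**What to change.** In all randomized sub-study participants with usable EEG, make the Aim 7 test a model of Week-6 PANSS total (or change) on:

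- treatment (pooled oxytocin versus placebo);
- baseline PANSS;
- continuous mu enhancement, defined as post-challenge minus pre-challenge;
- treatment × mu enhancement.

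With baseline in the model, Week-6 score and change give the same interaction coefficient. Report the mu slope with its 95% CI in each arm and label the test exploratory. Keep the planned correlations as descriptive, name each one Pearson or Spearman, and state which arms enter. Reconcile the two statements of the challenge dose before the marker is defined.

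The cost is wording: the measurements are already scheduled, and the plan already fits interactions of this kind for other baseline characteristics. The price is a more modest claim. At 30% to 59% power for a 0.5 SD slope difference, a non-significant interaction would not rule out a useful marker.

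### The only mu-suppression analysis that names improvement, an exploratory one, splits a continuous marker at the sample median and so gives up about 36% of its information

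*Combined protocol and SAP*

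**What the plan says.** Section 9 (Mu wave suppression paradigm) defines mu suppression as the log10 ratio of mu power under the experimental condition to mu power under the moving-ball condition. It is a continuous measure, and the sub-study is optional.

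The MU-Suppression paragraph under Statistical Consideration plans these analyses:

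- **Lead analysis:** a correlation between "mu wave suppression in response to a single dose of OT and symptom severity at the end of 6 weeks of treatment". The marker is not split. The outcome is a severity level.
- **Exploratory analysis:** introduced with "In additional exploratory analyses". Here "mu suppression values will be split at the median into High suppressors and Low suppressors", followed by correlations with symptom measures "to determine if initial high suppression is correlated with greater improvement in symptom severity".
- **Secondary analyses:** correlations "between mu wave suppression and symptom severity at baseline, and between mu wave suppression and symptom severity after administration of a single dose of oxytocin". Both outcomes are again severity levels.

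No baseline adjustment is described for any of these. The list of baseline moderators under Analysis Methods does not include mu suppression. No reason is given for the split, and no external cut point is cited.

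The question to be answered is set elsewhere. Aim 7 in section 6 asks whether enhancement of mu suppression "can serve as a predictive biomarker of individual clinical response to this neurohormone". Section 7 expects that "subjects with the greatest enhancement in mu suppression are more likely to experience clinical improvement", which is a graded hypothesis.

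**The concern.** The aim concerns response to treatment and the stated expectation is graded. Yet the one analysis whose outcome is improvement first reduces the marker to two groups. Every subject above the median then counts the same, however large the effect on mu suppression, and likewise below it. That costs power in a small optional sub-study.

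The cut point is also the median of whoever joins and has usable EEG. A later trial would have no independent reason to adopt it, although this pilot is meant to inform such trials.

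**Working it through.** The plan gives no sample size, effect size or power for the mu analyses, so there is no figure of its own to reproduce.

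**1. Does the lead correlation answer the improvement question?** Week-6 severity is baseline severity plus change, so

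cov(mu, week 6) = cov(mu, baseline) + cov(mu, change).

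If the first term is not zero, a week-6 correlation can appear when the marker says nothing about change. The plan itself expects a non-zero first term: section 7 reports that mu impairment correlates with negative symptoms, and a secondary objective in section 6 is to correlate mu deficits with symptom severity. The lead analysis is therefore not a continuous version of the improvement analysis.

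**2. Loss from the split.** Assume a normal marker X and a linear relation with outcome Y, with correlation r. The correlation of X with its own above/below-median indicator is √(2/π) = 0.798. So:

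- correlation after the split = 0.798 r
- relative efficiency = 2/π = 0.637
- information lost = 1 − 0.637 = 0.363, about 36%
- equivalent sample: 48 × 0.637 = 30.6, and 72 × 0.637 = 45.8

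**3. Sample size available.** The Sample Size Calculation gives 24 placebo and 48 oxytocin subjects, 72 in all. EEG participation is optional and its number is not stated. The ceiling is thus 72, or 48 if only oxytocin-treated subjects are used. The n = 36 row is an assumption: half of 72.

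**4. Power.** Assumptions: true r = 0.4, two-sided alpha 0.05. Formula: power = Φ(atanh(r) × √(n − 3) − 1.960).

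- Continuous: atanh(0.4) = 0.4236
- Split: 0.798 × 0.4 = 0.319, and atanh(0.319) = 0.331

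| n | √(n − 3) | Continuous | Median split |
|---|---|---|---|
| 36 | 5.745 | 68% | 48% |
| 48 | 6.708 | 81% | 60% |
| 72 | 8.307 | 94% | 78% |

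For other values of r, continuous against split:

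| n | r = 0.3 | r = 0.5 |
|---|---|---|
| 36 | 43% v 29% | 88% v 68% |
| 48 | 55% v 37% | 96% v 81% |
| 72 | 73% v 53% | 99.5% v 94% |

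For 80% power at r = 0.4, the continuous analysis needs 47 subjects and the split needs 75.

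**5. Simulation check** (20,000 bivariate normal samples, n = 48, r = 0.4):

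- Pearson: 82%
- Spearman: 77%
- High/Low split: 62% (60% if the outcome is ranked)
- correlation within one half (24 subjects): 23%

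The plan calls its correlations Pearson rank, a term that mixes two methods, so both comparators are shown. Against Spearman the loss is 77 − 62 = 15 points; against Pearson it is 82 − 62 = 20 points. The sentence on follow-up correlations could mean a High/Low indicator or separate correlations within each half. The 36% figure applies to the first reading; the second loses more.

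**The case against.** The strongest reply is that this is an additional, exploratory analysis in an optional sub-study of a pilot, and that the lead analysis keeps the marker continuous. That is true and it limits the importance of the point. A reader might infer that mu suppression is only ever analysed as two groups, or that an efficacy result is at risk. The documents support neither reading: three of the planned correlations leave the marker unsplit, and the PANSS treatment comparison does not use it.

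It can also be said that the deeper fault is the week-6 outcome in the lead correlation, and that the split would be a harmless supplement if that outcome were change. This stands, and for that reason the fix changes the outcome as well as the form of the marker.

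The split is not worthless either. Groups are easy to display, do not require a linear relation, and limit the influence of extreme log-ratio values. So it would be too strong to say that the split brings no benefit. It would also be too strong to say that the cut point cannot be carried over to a later trial. A median on a defined log10 scale can be reported and tested again; it is unvalidated, not unusable.

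Finally, a correlation of the marker with change cannot by itself separate prediction of response to oxytocin from general prognosis. This also stands, and the fix allows for it.

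**Conclusion.** The point holds as a minor one. The only planned mu analysis with improvement as its outcome uses a median split, and no unsplit analysis answers the same question.

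Under approximate normality and linearity, a High/Low split loses about 36% of the information. At an assumed r = 0.4 that costs between 16 points of power (n = 72: 94% to 78%) and about 21 points (n = 36: 68% to 48%, before rounding 68.2% to 47.6%; n = 48: 81% to 60%). The cost is about 15 points at n = 48 against a rank correlation, and more if correlations are run within halves.

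The value of r, the shape of the marker's distribution, alpha and the sub-study size are assumptions, since the documents give none of them for this analysis. The direction of the loss does not depend on the exact r. The primary and secondary efficacy conclusions are untouched.

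**What to change.** Rewrite the improvement analysis in the MU-Suppression paragraph:

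- **Marker:** define mu enhancement as the change in the log10 ratio from before to after the challenge dose, and keep it continuous. Name the video condition and electrode sites, and state which sign means greater suppression.
- **Outcome:** PANSS total change from baseline to week 6, adjusted for baseline PANSS.
- **Subjects:** oxytocin-treated subjects. If placebo subjects are included (the schedule footnote gives every subject the challenge dose), add treatment and a treatment-by-mu term. That term addresses prediction of response to oxytocin as distinct from prognosis. Report it with its confidence interval, since at this size it will be imprecise.
- **Correlation type:** say Pearson or Spearman.
- **High/Low groups:** use for plots only.

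The cost is a few sentences in the SAP, settled before unblinding. EEG before and after the challenge dose and weekly PANSS are already scheduled, so no visits, subjects or measurements are added.
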